2.2 Endpoints

Primary Endpoint

- Cumulative rate of any spontaneous abortion occurring on or before 12 weeks following oocyte retrieval in all subjects treated with PVR and undergoing fresh embryo transfer.
Note: spontaneous abortion is defined as two positive β -hCG tests occurring at least two days apart on or after 2 weeks post-oocyte retrieval, but followed by observation of any empty intrauterine gestational sac (blighted ovum), intrauterine gestation without a fetal heart beat, or absence of viable fetuses, as documented by transvaginal ultrasound (TVUS).

Secondary Endpoints

- Cumulative rate of spontaneous abortions determined at 6 and 10 weeks post-oocyte retrieval in all subjects treated with PVR.
- Cumulative rate of biochemical abortions determined at 6 and 10 weeks post-oocyte retrieval in all subjects treated with PVR. Biochemical abortion is defined as a positive β -hCG test at 2 weeks and 2 weeks + 3-4 days post-oocyte retrieval, but followed by no observed gestational sac on a later TVUS, or followed by a negative β -hCG test.
- Rate of ectopic and heterotopic pregnancies in all subjects treated with PVR following oocyte retrieval.
- Rate of abnormal findings in clinical laboratory tests and vital signs for all subjects treated with PVR.
- Frequency, intensity/grade, seriousness, and relatedness of adverse events (AEs) for all subjects treated with PVR.
- Frequency, intensity/grade of vaginal bleeding/spotting, vaginal hemorrhage, pain, vaginal infection, and vaginal irritation for all subjects treated with PVR.
- Frequency, intensity/grade, seriousness, and relatedness of AEs associated with vaginal and cervical abrasions and lesions and with vaginal adhesions for all subjects treated with PVR.
- Frequency and reason for PVR discontinuation.
- Positive β -hCG rate (positive serum β -hCG test) at 2 weeks and 2 weeks + 3-4 days post-oocyte retrieval in all subjects treated with PVR.
- Clinical pregnancy rate (TVUS showing at least 1 intrauterine gestational sac with fetal heart beat) at 6 and 10 weeks post-oocyte retrieval in all subjects treated with PVR.

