Oocyte retrieval will occur approximately 35-37 hours after hCG administration. On the day after oocyte retrieval, the subject will begin treatment with the IMP, PVR. Following instruction on PVR insertion and removal (see [Appendix 1](#)), the subject will insert the first PVR (PVR1) at the trial site. The PVR will remain in place a minimum of 23 hours/day. The subject will remove PVR1 before embryo transfer and reinsert it after the transfer. Fresh embryo transfer will occur 5 days after oocyte retrieval per the trial site's protocol. The number of embryos to transfer must be guided by the 2017 American Society for Reproductive Medicine (ASRM) and the Society for Assisted Reproductive Technology (SART) guidelines (SART/ASRM 2017): women with the expectation of one or more high-quality embryo(s) available for cryopreservation, and women with previous live birth after an IVF cycle, will have transfer of a single blastocyst. All other women will have transfer of no more than two blastocysts. Additional PVRs will be distributed for weekly insertion, with the second PVR (PVR2) to be inserted at home 7 days following the initial insertion of the first PVR (PVR1), and the third PVR (PVR3) to be inserted either at home or at the site 7 days following the insertion of PVR2.

Two weeks after oocyte retrieval, a blood draw will be performed to measure serum levels of progesterone and β -hCG. Subjects with a β -hCG level <5 mIU/mL will be discontinued from the trial. Those with a β -hCG level ≥ 5 mIU/mL will insert their next PVR and continue in the trial for up to a total of 10 weeks (up to a total of 10 PVRs). Additional serum pregnancy tests will be performed at 2 weeks + 3-4 days and at 3 weeks. Subjects who are no longer pregnant will be discontinued from the trial. Subjects with positive β -hCG results at 3 weeks will insert PVR4 and receive PVR5 and PVR6 to be inserted weekly.

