7 TRIAL ASSESSMENTS

7.1 Assessments Related to Primary Endpoint

7.1.1 Pregnancy Monitoring

7.1.1.1 **β-hCG Test**

Serum pregnancy tests will be obtained at 2 weeks, 2 weeks + 3-4 days, and 3 weeks after oocyte retrieval (i.e. at Visits 6, 6P, and 7). Subjects with a β -hCG level <5 mIU/mL will be discontinued from the trial.

7.1.1.2 **Transvaginal Ultrasound**

A TVUS will be performed at 4 weeks + 3-4 days after oocyte retrieval (Visit 7P) to document the presence of an intrauterine gestational sac, and at 6 weeks after oocyte retrieval (Visit 8) to determine the presence and number of gestational sacs with/without fetal heart beat. Ten weeks after oocyte retrieval (Visit 9), either a TVUS or abdominal ultrasound will be performed in pregnant subjects to determine the presence and number of gestational sacs with/without fetal heart beat and to estimate gestational age.

7.1.1.3 **Ectopic and Heterotopic Pregnancies**

If, at the TVUS performed 4 weeks + 3-4 days after oocyte retrieval, it is determined that the subject has an ectopic pregnancy, the subject will be treated according to the site's standard protocol and will be withdrawn from the trial.

If it is determined that the subject has a heterotopic pregnancy, the subject will be treated according to the site's standard protocol and may remain in the trial at the discretion of the Investigator.

7.1.2 **Spontaneous Abortion**

Spontaneous abortion is defined as two positive β -hCG tests occurring at least two days apart on or after 2 weeks post-oocyte retrieval, but followed by observation of any empty intrauterine gestational sac (blighted ovum), intrauterine gestation without a fetal heart beat, or absence of viable fetuses, as documented by ultrasound.

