8.3.7 Pregnancy Losses

Cases of biochemical abortion, spontaneous abortion, ectopic pregnancy and heterotopic pregnancy will be recorded as AEs.

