### 9.2 Primary Endpoint

The primary endpoint, spontaneous abortion, is defined as two positive  $\beta$ -hCG tests occurring at least two days apart on or after 2 weeks post-oocyte retrieval, but followed by observation of any empty intrauterine gestational sac (blighted ovum), intrauterine gestation without a fetal heartbeat, or absence of viable fetuses, as documented by transvaginal ultrasound (TVUS).

The derivation of this endpoint will be as follows:

- Any subject that has two positive  $\beta$ -hCG tests at least two days apart, and
- meeting at least one of the following conditions at visit 7P (4 weeks and 3-4 days post oocyte retrieval) or at a later visit:
  1. the TVUS assessment at a later visit shows that there is no presence of gestational sac,
  2. there is a presence of empty gestational sac,
  3. there is a gestational sac that has a fetus without a heartbeat, or
  4. any AE of pregnancy loss that meets the definition of spontaneous abortion.

In order to clearly identify AEs that are spontaneous abortions, listing of all AEs related to pregnancy loss, will be generated and provided to the medical team together with the reported and coded terms. [Appendix 3](#) lists the preferred terms associated with pregnancy loss that will be used for generating this listing. This listing will be provided periodically throughout the trial. The medical team will use these listings to identify AEs that meet the spontaneous abortion definition. The identification process will be completed prior to data base lock. Since spontaneous abortion can occur outside of scheduled visits, for accurate accounting of all spontaneous abortions, the AE eCRF page needs to be included.

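### SAP 9.2 contradicts itself and the protocol on the earliest time a spontaneous abortion can count: read literally, a loss documented before Visit 7P may be left out of the primary rate

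*SAP*

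**What the plan says.** **Protocol definition (2.2, 7.1.2, 9.7.2).** Two positive β-hCG "tests occurring at least two days apart on or after 2 weeks post-oocyte retrieval", then "followed by observation of any empty intrauterine gestational sac (blighted ovum), intrauterine gestation without a fetal heart beat, or absence of viable fetuses" on ultrasound. The finding must follow the two tests. No visit or date is set before which it cannot count.

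**SAP 9.2, definition.** The section opens with the same definition, again with no earliest date.

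**SAP 9.2, derivation.** A subject counts if she has two positive tests and is "meeting at least one of the following conditions at visit 7P (4 weeks and 3-4 days post oocyte retrieval) or at a later visit". Four numbered conditions follow. The first three are ultrasound findings: no sac, an empty sac, or a fetus without a heartbeat. The fourth is "any AE of pregnancy loss that meets the definition of spontaneous abortion". All four stand under the one lead-in.

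**SAP 9.2, closing text.** Listings of pregnancy-loss AEs go to the medical team, which identifies those meeting the definition before database lock. The stated reason: "Since spontaneous abortion can occur outside of scheduled visits, for accurate accounting of all spontaneous abortions, the AE eCRF page needs to be included".

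**Related protocol text.** Section 8.3.7: "Cases of biochemical abortion, spontaneous abortion, ectopic pregnancy and heterotopic pregnancy will be recorded as AEs". Section 3.1.2: "Subjects who are no longer pregnant will be discontinued from the trial". A Table 6-1 footnote waives the ultrasound at an early-withdrawal visit when the subject is no longer pregnant.

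SAP section 12, which lists changes from the protocol, does not mention the Visit 7P condition.

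**The concern.** The primary safety result is a count of losses whose exact upper limit is compared with 15%. A timing rule that appears in the derivation but not in the definition can remove real events from that count.

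Take a woman with positive tests at Visits 6 and 6P who bleeds in the fourth week after retrieval and has an unscheduled scan showing an empty sac. She meets the protocol definition. She is discontinued as no longer pregnant, and no later scan is required. A programmer who follows the SAP list as printed has no ultrasound finding at or after Visit 7P, and her AE is dated before it. She does not clearly fall under biochemical abortion either (protocol 7.2.3, SAP 9.4.2): a sac was seen, and the last scheduled β-hCG is at Visit 7.

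For such losses the error runs one way only. It lowers the observed rate and makes it easier to exclude 15%.

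**Working it through.** **1. Length of the gap (nominal days after retrieval)**

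- Visit 6, first β-hCG: Day 14 (protocol 6.3.3).
- Visit 6P, second β-hCG: 14 + 3 to 4 = Day 17-18 (6.3.4).
- Visit 7, third β-hCG: Day 21 (6.3.5).
- Visit 7P, first scheduled pregnancy ultrasound: 21 + 7 + 3 to 4 = Day 31-32 (6.3.6).

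For about two weeks, then, a loss can satisfy the protocol definition without satisfying the SAP list read literally.

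**2. Two readings of the AE route**

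| | Loss AE before Visit 7P |
|---|---|
| Condition 4 read under its lead-in | not counted |
| Condition 4 read for its stated purpose | counted |

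Both readings come from SAP 9.2, and nothing in the section says which governs.

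**3. Reproducing the plan's power**

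Inputs: mITT N = 240, two-sided exact 95% interval, threshold 15%, assumed true rate 9% (SAP 3.3 and 9.3.1).

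The Clopper-Pearson upper limit for x events is the 0.975 quantile of Beta(x + 1, 240 − x).

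- x = 25 (10.42%): upper limit 14.99%, which excludes 15%.
- x = 26 (10.83%): upper limit 15.47%, which does not.

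Power = P(Bin(240, p) ≤ 25):

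| True rate p | Exact | SAP Table 2 (simulated) |
|---|---|---|
| 8% | 92.9% | 93.1% |
| 9% | 81.3% | 81.8% |
| 10% | 63.6% | 63.2% |

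The plan's figures reproduce within simulation error.

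**4. What an undercount would do**

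One uncounted loss lowers the rate by 1/240 = 0.42 percentage points. If a share f of losses goes uncounted, the effective rate at a true 15% is 0.15 × (1 − f), and the chance of excluding 15% is P(Bin(240, 0.15(1 − f)) ≤ 25). The documents give no value for f, so these shares are assumptions.

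| f | Effective rate | Expected missed (240 × 0.15 × f) | Chance of excluding 15% |
|---|---|---|---|
| 0 | 15.0% | 0 | 2.5% |
| 2% | 14.7% | 0.7 | 3.3% |
| 5% | 14.25% | 1.8 | 5.0% |
| 10% | 13.5% | 3.6 | 9.3% |

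**5. How often the true count lies just above the limit**

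P(X = 26) is 5.2% at a true 9% and 7.5% at a true 10%. P(26 ≤ X ≤ 28) is 12.3% and 19.8%. These are chances that the count falls where one to three missed losses would matter. They are not chances that the result changes, which also needs that many losses to fall in the gap.

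**The case against.** The strongest reply is that the SAP already counts these losses. Section 9.2 opens with the definition free of any visit condition, the medical team judges AEs against that definition, and the section gives complete counting as its reason for using the AE page. The protocol makes every loss an AE. The visit label may also be met: an early withdrawal is Visit 9 and an End-of-trial visit follows, AEs are recorded at both, and both come after Visit 7P in the schedule.

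This stands in part. A reader might infer that the SAP excludes every loss before Visit 7P, or that SAP and protocol define two different endpoints. The documents do not support either: the text is contradictory, and its stated purpose favours counting. The reply still does not lift the lead-in from condition 4, and a program written from the list could drop the event.

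The group is also narrow, and that stands. No pregnancy scan is scheduled before Visit 7P. The subject needs two positive tests, an unscheduled scan with a qualifying finding and no qualifying scan afterwards. A sac still abnormal at Visit 7P is counted there. A loss shown only by β-hCG turning negative is biochemical in both documents. A large undercount is therefore unlikely. A missed share of 20%, for example, would mean about 7 of 36 losses at a true 15% (0.20 × 36 = 7.2), with a 26.1% chance of excluding 15%. Nothing in the documents points to that.

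A timing rule for scan findings is itself defensible. The Visit 7P scan documents a sac, and heartbeat is first a scheduled assessment at Visit 8, so an early scan could mislabel a viable pregnancy.

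Lastly, protocol section 2 says the primary label sets priority and does not tie the trial's success to this endpoint. That lowers the severity, but the comparison with 15% is still planned and will be reported.

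**Conclusion.** SAP 9.2 does not settle whether a loss documented between the second positive test (about Day 17-18) and Visit 7P (about Day 31-32) counts. Its list says no, its stated purpose says yes, and the protocol definition has no such condition. The literal reading may leave out a loss seen on an unscheduled scan in a woman withdrawn without a later one.

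The number affected is unknown and probably small. For these losses the direction is certain: the rate can only fall. The decision limit leaves no slack, since 25 events pass and 26 do not. The rise from 2.5% to 3.3, 5.0 or 9.3% depends wholly on the assumed shares of 2, 5 and 10%, with the low end more plausible.

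This does not establish the net bias of the whole derivation. Condition 1 (no sac) overlaps the biochemical abortion definition and could push the count upward; that is a separate question. The point should be fixed, but it does not invalidate the design.

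**What to change.** In SAP 9.2:

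- Apply the Visit 7P timing to scheduled-scan conditions 1-3 only.
- Move condition 4 out from under that lead-in as a separate route.
- State that a loss recorded as an AE and judged by the medical team to meet the protocol definition, including one documented on an unscheduled scan, counts from the second positive β-hCG test through 12 weeks after retrieval, unless a later scan shows a fetal heartbeat.

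The heartbeat proviso guards against counting an early viable pregnancy. It is not in the protocol definition, so it should be listed in SAP section 12.

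**Cost.** One SAP sentence and the matching derivation program, before database lock. No new visits are needed, and the AE page and medical review are already planned. N = 240 and the stated power do not change. The observed rate may come out slightly higher. An early finding with no later scan will rest on the medical team's judgement, because the proviso cannot help there. The documents do not say how unscheduled scans are captured in the eCRF, so the fix relies on the AE record, as SAP 9.2 already does.

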6.3.5 Visit 7: Week 5 of Pregnancy (3 Weeks After Oocyte Retrieval)

Subjects will attend Visit 7, 3 weeks (21±2 days) after oocyte retrieval.

The following must take place at the visit:

- Vital signs
- Blood collection for assessment of:
 - Endocrine parameters (β -hCG)
If the subject has a negative β -hCG (<5 mIU/mL), treatment will be stopped and the subject will be withdrawn from the trial and the early withdrawal visit is to occur (section 6.3.8).
- Removal of PVR3 and insertion of PVR4 (for subjects with a positive β -hCG (\geq 5 mIU/mL))
Insertion of PVR4 can be performed either at the trial site or at home.
- Review of PVR diary
- Assessment of drug accountability
- Recording of any vaginal bleeding noted in the subject's bleeding log since the previous visit
- Assessment of vaginal hemorrhage
- Recording of use of any concomitant medication
- Recording of AEs
- Dispensing of IMP: the next 3 PVRs and a replacement PVR to be used in the event of ring loss or damage (PVR5, PVR6, PVR7 and PVR-R) will be distributed.
The subjects will remove and insert the PVRs at home. Subjects will be instructed to replace the PVR every 7 days. If the replacement PVR is used, the subject should obtain another replacement PVR from the trial site as soon as possible.

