6.3.6 Visit 7P: Procedural Visit

Subjects will attend a procedural visit (Visit 7P), one week + 3-4 days after Visit 7.

The following must take place at the visit:

- TVUS to document the presence of an intrauterine gestational sac.
In case of an ectopic pregnancy the subject will be treated according to the site's standard protocol. Treatment with PVR will be stopped and the subject will be withdrawn from the trial and the early withdrawal visit is to occur (section 6.3.8).
- Pelvic examination (documentation of presence and grade [intensity] of any pain, irritation, abrasions, or lesions on the cervix or vagina or vaginal adhesions).

If any lesions or abrasions are found on the cervix or vagina or vaginal adhesions are noted, another examination will be performed 2-4 days later.

- Review of PVR diary
- Recording of any vaginal bleeding noted in the subject's bleeding log since the previous visit
- Assessment of vaginal hemorrhage
- Recording of use of any concomitant medication
- Recording of AEs

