9.7.2 Primary Endpoint

The primary endpoint is the cumulative rate of any spontaneous abortion occurring on or before 12 weeks following oocyte retrieval in all subjects treated with PVR and undergoing fresh embryo transfer. Spontaneous abortion is defined as two positive β -hCG tests occurring at least two days apart on or after 2 weeks post-oocyte retrieval, but followed by observation of any empty intrauterine gestational sac (blighted ovum), intrauterine gestation without a fetal heart beat, or absence of viable fetuses, as documented by ultrasound.

In addition to the analysis specified in section 9.1, the number and rates of any spontaneous abortions (occurring on or before 12 weeks following oocyte retrieval) in all subjects in the mITT cohort will be analyzed as a sensitivity analysis using a Bayesian hierarchical model to dynamically borrow information from the DR-PGN-302 study. The cumulative rate of any spontaneous abortion from Study DR-PGN-302 was 55/549 (10.2%). Dynamic borrowing between this prior data and the current trial's data allow borrowing to occur to the extent indicated by these two observed rates. More borrowing occurs when the rates are similar while less when they differ. Full modeling details are provided in [Appendix 6](#).

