## Change log

Version No.	Effective Date	Reason for the Change / Revision	Supersedes
1.0	May 11, 2018	NA	None
2.0	Oct 08, 2018	

• To make the SAP consistent with the protocol amendment.

• More detailed analysis of embryo quality has been added.

• More details have been added to the analysis of bleeding logs.

• Typographical and formatting errors have been corrected.

	1.0
3.0	Feb 26, 2019	

• Responded to FDA feedback on statistical design by adjusting confidence intervals and assuring that endpoints align with the DR-PGN-302 study

• Updated the document author to reflect the new statistician

• Corrected formatting issues, typos, text relating to which drug was used for hCG triggering, and “Other Endpoint(s)” to “Other Assessment(s)”

• Added tabulation of vaginal hemorrhage (was in protocol, but not SAP)

• Clarified the use of Preferred Terms, how baseline is calculated for laboratory and vital signs variables, how shift tables are to be calculated, and the tabulation of bleeding log data for non-completers.

	2.0

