### 9.4.2 Biochemical Abortions within 6 and 10 Weeks of Oocyte Retrieval

Biochemical abortion is defined as a positive  $\beta$ -hCG test (at 2 weeks and 2 weeks + 3-4 days post-oocyte retrieval) but followed by no observed gestational sac on a later TVUS, or followed by a negative  $\beta$ -hCG test. Additionally, a biochemical abortion can be defined by an AE that meets the definition of biochemical abortion (see [Appendix 3](#)). To allow for assessment that might occur outside the visit window, a subject will be considered to be biochemically pregnant if there are two positive assessments at least two days apart on or after 2 weeks post-oocyte retrieval.

The frequency and proportion of subjects that have biochemical abortion within 6 and 10 weeks (i.e., up to 42 and 70 days) post-oocyte retrieval will be derived for subjects in the mITT and safety cohorts for subjects that had oocyte(s) retrieved. Associated 95% confidence intervals will also be presented.

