### 9.4.3 Ectopic and Heterotopic Pregnancies

At time of TVUS examination, ectopic and heterotopic pregnancies may be detected and recorded in the TVUS eCRF. These events may also occur outside such assessment visits and may be recorded in the AE CRF. The preferred terms associated with ectopic pregnancy are presented in [Appendix 3](#) and will be used to select and check for such terms. The frequency and proportion of subjects with ectopic and heterotopic pregnancies will be pooled from the two sources and summarized.

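### As worded, SAP 9.2 condition 1 can put never-sac losses and no-sac ectopic pregnancies into the primary spontaneous abortion rate, while SAP 9.4.2 and 9.4.3 count the same women again.

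*SAP*

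**What the plan says.** **Primary endpoint (SAP 9.2, 9.3).** A woman is an event if she has two positive β-hCG tests at least two days apart and meets at least one of four conditions at Visit 7P or later. Condition 1 is that "the TVUS assessment at a later visit shows that there is no presence of gestational sac". Conditions 2 and 3 are an empty sac and a fetus without a heartbeat. Condition 4 is a pregnancy-loss AE that the medical team judges to meet the definition. The cohort is mITT and the window is 12 weeks from oocyte retrieval.

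**Biochemical abortion (SAP 9.4.2).** The β-hCG requirement is in effect the same: two positives at least two days apart, from week 2 onward. The outcome is either "followed by no observed gestational sac on a later TVUS" or a later negative β-hCG. The windows are 42 and 70 days, and the cohorts are mITT and safety. There is also an AE route: "Additionally, a biochemical abortion can be defined by an AE that meets the definition of biochemical abortion".

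**Ectopic pregnancy (SAP 9.4.3).** At the scan, "ectopic and heterotopic pregnancies may be detected and recorded in the TVUS eCRF". These are pooled with AE reports. Nothing removes the women from 9.2 or 9.4.2.

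**Distinct events elsewhere.** Protocol 8.3.7 lists biochemical abortion, spontaneous abortion, ectopic and heterotopic pregnancy separately and has each recorded as an AE. Protocol 9.9.5 names spontaneous and biochemical abortion as a primary and a secondary endpoint respectively.

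**Earlier trial.** Protocol 9.7.2 and SAP 9.3.2 use 55/549 from DR-PGN-302 for borrowing and do not give its counting rule. The change log for SAP 3.0 speaks of "assuring that endpoints align with the DR-PGN-302 study".

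**The concern.** The primary objective is to estimate a rate, and its numerator depends on how condition 1 is read. Two programmers following SAP 9.2 could reach different counts: one would include every no-sac scan after two positive tests, the other only a sac that was seen and then gone. The reader of the report could not tell which was done, nor whether the spontaneous, biochemical and ectopic rates share women.

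Two uses of the rate are exposed. The upper limit of its exact interval is assessed against 15%. The sensitivity analysis pools it with 55/549, which is meaningful only if both trials counted losses in the same way.

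**Working it through.** **1. The two rules side by side**

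| Element | SAP 9.2, condition 1 | SAP 9.4.2, TVUS limb |
|---|---|---|
| β-hCG | two positives, at least 2 days apart | two positives, at least 2 days apart |
| Scan | no gestational sac | no gestational sac |
| Earlier sac required? | not stated | not stated |
| Cohort | mITT | mITT and safety |
| Window | 12 × 7 = 84 days | 42 and 70 days |

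The Visit 7P scan, whose purpose is "TVUS to document the presence of an intrauterine gestational sac", falls at 28 + 3 to 28 + 4 = day 31 to 32 after retrieval. That is inside all three windows.

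**2. Who can be affected**

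- A woman with a negative β-hCG at Visit 6, 6P or 7 leaves before 7P. At Visit 7, for example, "treatment will be stopped and the subject will be withdrawn from the trial and the early withdrawal visit is to occur". Footnote j of protocol Table 6-1 requires no ultrasound at an early withdrawal visit once she is no longer pregnant. Most early biochemical losses are therefore outside the overlap.
- A woman still positive at Visit 7 with no sac on TVUS can meet both rules.
- A woman with an ectopic pregnancy is withdrawn (protocol 7.1.1.3) but stays in mITT, which needs only retrieval, one dose and transfer. If her scan record shows no sac, she can meet 9.2 and 9.4.2 and is also counted under 9.4.3. A recorded extrauterine sac would not literally meet condition 1. SAP Appendix 3 lists abortion of ectopic pregnancy under both the spontaneous abortion and the ectopic terms.

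**3. The plan's own power figure**

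Inputs: n = 240, threshold 15%, two-sided exact 95% interval, assumed rate 9% (SAP 3.3). The upper limit for x events is the 0.975 quantile of Beta(x + 1, n − x).

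- x = 25: 14.99%
- x = 26: 15.47%

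At most 25 events are allowed. P(X ≤ 25 | 240, 0.09) = 81.3%, against a simulated 81.8% in SAP Table 2. The figure reproduces. At n = 215, the other transfer figure in protocol 3.5.1, the turn lies between 21 events (14.54%) and 22 (15.08%).

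**4. Illustration only, because the number of affected women is unknown**

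(a) Assume k affected women on top of a narrow count X ~ Bin(240, 0.09). The two counts lead to different assessments when 26 − k ≤ X ≤ 25.

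| k | 1 | 2 | 3 | 4 |
|---|---|---|---|---|
| Probability | 6.3% | 13.8% | 22.1% | 30.9% |

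(b) Assume instead that the 9% already includes them, which is the more direct reading of SAP 3.3. Power for the broad count stays at 81.3%. The counts are nested, so they disagree with probability P(X ≤ 25 | narrow rate) − P(X ≤ 25 | 0.09). For a share of 0.5 point this is 0.8791 − 0.8126, about 6.7%. For 1 point it is 0.9285 − 0.8126 = 11.6%.

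(c) If the rate including these women is truly 15%, the chance of excluding 15% is P(X ≤ 25 | 240, 0.15) = 2.5% with the broad count. It is 4.0% if 0.5 point is left out (rate 14.5%) and 6.2% if 1 point is left out (rate 14%).

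**5. The earlier trial's figure**

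55/549 = 10.02%. The 10.2% printed in protocol 9.7.2 equals 56/549, so the count needs a look-up in any case.

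**The case against.** **Wording of condition 1.** The lead-in already sets Visit 7P or later. Condition 1 repeats the reference to a later visit, and conditions 2 and 3 do not. The repeat may mean a scan after 7P, or after an earlier sac. On either reading a no-sac scan at 7P alone does not qualify, and few never-sac women would be scanned again. This stands: the plain reading is not the only one. It does not remove the ambiguity.

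**Medical review.** Protocol 8.3.7 has every such loss recorded as an AE, and the medical team sorts the pregnancy-loss AEs before database lock. This narrows the gap. But the review serves condition 4. Condition 1 is driven by the scan, and no text says that an AE of biochemical abortion overrides it.

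**Overlap need not be an error.** The rates are reported separately and are not summed. The definition includes the absence of viable fetuses, so a broad primary count may be intended. This also stands, and it is a reason to confirm the broad count and not replace it.

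**Stronger readings that the documents do not support.**

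- A reader might infer that biochemical losses in general enter the primary rate. The withdrawal rules keep most of them out.
- A reader might infer that a woman whose sac was seen and later lost is also a biochemical abortion. That strains 9.4.2, because in her case a sac was observed.
- A reader might infer that the trial is underpowered. That holds only if the assumed 9% excludes these women, which is the less direct reading of SAP 3.3. Under it, exact power would fall from 81.3% to 73.0% (0.5 point added) or 63.6% (1 point added).

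**Conclusion.** The point holds as a defect in a stated rule. On its plain reading, condition 1 can admit never-sac losses and no-sac ectopic pregnancies to the primary numerator. Other sections count the same women again, although the protocol treats the events as distinct. It should be fixed, but it does not invalidate the plan.

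Its size cannot be fixed from the documents. What is certain is the leverage at the turning point: one woman moves the upper bound from 14.99% to 15.47% at n = 240. The percentages in step 4 of the working rest on assumed numbers of cases.

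The direction is conservative. Extra events make it harder to exclude 15%, and section 2 of both documents says that trial success is not tied to this endpoint. A reader might infer that the rule flatters the product; the documents do not support that. The risk of too favourable a result would come from narrowing the count late. The trial is open-label, pregnancy-loss listings circulate during it, SAP 4.0 is dated 9 August 2019, and the last visit was estimated for the third quarter of 2019.

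**What to change.** Before database lock, and without reference to the counts:

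1. State in SAP 9.2 that the primary count is the literal broad one: any no-sac TVUS after two positive β-hCG tests, including never-sac and no-sac ectopic cases, alongside the other conditions.
2. Add a supportive analysis, with its exact 95% interval, that requires a documented intrauterine sac or a medically confirmed clinical loss. This excludes never-sac and no-sac ectopic cases.
3. State in SAP 9.4.2 and 9.4.3 that the categories may overlap, tabulate the overlap, and say which source prevails when the AE and the TVUS disagree.
4. State the counting rule behind 55/549 if it can be recovered, and run the borrowing model on the matching version. If it cannot be recovered, run the model on both. Correct the printed percentage or the count at the same time.

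The cost is wording in three SAP sections, one look-up and a little programming. No new data are needed. The downside is that two versions of the rate appear in the report and must be clearly labelled as primary and supportive.
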